## 6. Statistical Considerations and Analysis

The primary efficacy endpoint to be evaluated in this study is the outcome of treated aneurysms from study subjects achieving Raymond Grade I (100% occlusion) at 12 months  $\pm$  8 weeks in the absence of retreatment, parent artery stenosis (> 50%), or target aneurysm rupture. The rate of the primary efficacy endpoint will be formally compared to a historical control, which is derived using a meta-analysis of the three very recent studies that specifically address bifurcating wide-neck basilar or MCA aneurysms (Fargen et al, 2013; Spiotta et al, 2011; and Zhang et al, 2014) as summarized in the Table 6-1. The study will be conducted at up to 28 centers and will enroll up to 159 subjects to ensure treatment/attempted treatment of 119 subjects (107 evaluable assuming a 10% loss to follow-up rate).

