## 6.2 Primary Analysis

The goal of the primary analysis will be to demonstrate that the Barrel® VRD device performs better than the combined historical control treatments for complete occlusion rate at 12 months. The hypothesis to be tested is:

$$H_0: \pi_B = \text{HC} \text{ versus } H_A: \pi_B > \text{HC}$$

Where  $\pi_B$  is the proportion of successful outcomes for the Barrel® VRD device and HC is the combined overall historical control success rate. Success is defined as a subject with a Raymond Grade of 1 (100% occlusion) at 12 months  $\pm$  8 weeks in the absence of retreatment, parent artery stenosis (> 50%), or target aneurysm rupture. This hypothesis will be tested using an exact one sample binomial test at ( $\alpha = 0.025$ ). Exact 95% confidence intervals will be constructed.

The meta-analysis analysis mentioned above provides an overall estimate for historical control success rate of 42.48% with a 95% confidence interval of (31.90%, 53.06%).

Although the meta-analysis provides the basis for deriving a historical control success rate, it does not allow exact comparison due to the author-evaluated Raymond Grades used in the studies versus the proposed core laboratory grade reporting. Moreover, the reported rates in the published literature do not take into account patients lost to follow-up in their final calculation of occlusion rates. Conversely, the Barrel study employs a more stringent intent-to-treat (ITT) methodology that treats those patients lost to follow up as treatment failures. A review of the literature shows that onsite angiographic evaluators report 20 to 60% higher Raymond Grade success rates than those reported by core laboratories. Rezek et al. (2013) states “Core laboratories tend to report higher rates of unfavorable outcomes compared with self-reporting centers. Indeed, the rate of unfavorable outcomes was 43.6% greater in core laboratories compared with noncore laboratory studies.” McDougall CG et al. (2014) states, “in 36% of cases, the local investigators reported a better degree of occlusion than did the core laboratory.”

Unfortunately only one paper, Rezek et al. (2014), provided sufficient detail of the operator and core laboratory

results, in a population that is representative of the patient population that is proposed in the protocol, to allow statistical analysis of the difference.

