### 6.3 Sample Size Calculation

In actuality, the real objective of this study is to demonstrate that the Barrel® VRD is comparable to historical controls. Therefore the historical success rate of 28% was selected as the historical control value. The Barrel® VRD will be considered successful if its lower 95% confidence limit is greater than 28%.

Table 6-2 presents the sample size necessary to have an 80% power with a significance level of 2.5% for rejecting the null hypothesis in favor of the alternative when the true success rate for the Barrel® VRD is as specified. The hypotheses to be tested are:

$$H_0: \pi_B = 28\% \text{ versus } H_A: \pi_B > 28\%$$

Where  $\pi_B$  is the proportion of successful outcomes for the Barrel® VRD device.

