### 6.5 Statistical Analysis Sets

The primary analysis set will be based on the intention-to-treat (ITT) population set. For this study, all subjects who meet the study entry criteria, sign the written informed consent (enrolled), and undergo attempted delivery with the Barrel VRD will be counted in the primary analysis set of ITT.

Analysis will also be performed on the per-protocol population set, defined as all subjects included in the ITT population set who have complied with the protocol without major protocol deviations, and have completed the 12-month angiographic evaluation.

The primary analyses for both the safety and effectiveness endpoints will be based on the observed data.

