## 6.10 Handling of Missing Data

Multiple imputation technique will be implemented to assess the impact of missing data on the analysis of efficacy endpoint. For the parameters summarized based on the incidence, an imputed dataset where the binary outcome for subjects who withdraw prior to the scheduled assessment will be derived using the Markov Chain Monte Carlo (MCMC) algorithm specifying missing at random (MAR). The subject characteristics and demographic factors to be included in the multiple imputation procedure to generate the imputed datasets for analysis will be defined in the Statistical Analysis Plan (SAP).

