### 8.1 Primary Outcome Measures

#### 8.1.1 Primary Endpoints

- Primary Efficacy Endpoint: The number of Barrel® VRD treated aneurysms achieving Raymond Grade I (100% occlusion) at 12 months  $\pm$  8 weeks in the absence of retreatment, parent artery stenosis ( $> 50\%$ ), or target aneurysm rupture. The primary efficacy endpoint will be met if the lower bound of the 95% confidence interval is  $> 23\%$ .
- Primary Safety Endpoint: Incidence of neurological death or major ipsilateral stroke (National Institutes of Health Stroke Scale [NIHSS] increase of  $\geq 4$  for  $>24$  hours) at any time during the follow-up period (12 months  $\pm$  8 weeks). The primary safety endpoint will be met if the upper bound of the confidence interval is  $\leq 15\%$ .

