### 12.6.5 Follow-Up (30-day, 180-day, and 12-month)

The following assessment will be completed at the specified time points below. All visits should be completed by study subjects with successful implant of the Barrel VRD. Subjects that underwent attempted delivery with the Barrel VRD, but were not implanted should complete the 30-day visit and be exited from the study.

- 30 Day  $\pm$  14 Days
  - Neurologic Evaluation
    - The Investigator is responsible for ensuring that the administration of the modified Rankin Score is conducted by a trained person with appropriate qualifications to perform these evaluations.
  - Details of any additional (subsequent) procedures or additional treatments
  - Description of adverse events, including the time of onset
  - Medication Usage
  - 30 day evaluations may be performed remotely via telephone if subject is not available for a visit to the study center.

- 180 Day  $\pm$  30 days
  - Neurologic Evaluation
    - The Investigator is responsible for ensuring that the administration of the NIHSS and modified Rankin Score are conducted by a trained person with appropriate qualifications to perform these evaluations.
  - Details of any additional (subsequent) procedures or additional treatments
  - Angiographic assessment (if done as standard of care)
    - Stenosis
    - Raymond grade
  - Description of adverse events, including the time of onset
  - Medication Usage
- 12 month  $\pm$  60 days
  - Neurologic Evaluation
    - The Investigator is responsible for ensuring that the administration of the NIHSS and modified Rankin Score are conducted by a trained person with appropriate qualifications to perform these evaluations.
  - Details of any additional (subsequent) procedures or additional treatments
  - Angiographic assessment
    - Stenosis
    - Raymond grade
  - Description of adverse events, including the time of onset
  - Medication Usage

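### Failed implants are in the primary ITT set but are exited at day 30, and no rule scores them as efficacy failures, so the observed-data analysis tends to drop them from the denominator

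*Protocol*

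**What the plan says.** Five parts of the protocol bear on this.

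- **Analysis set (6.5).** Eligible, consented subjects who "undergo attempted delivery with the Barrel VRD will be counted in the primary analysis set of ITT". A failed implant is therefore in the primary set by design. The same section bases the primary safety and effectiveness analyses on observed data.
- **Follow-up (12.6.5).** "Subjects that underwent attempted delivery with the Barrel VRD, but were not implanted should complete the 30-day visit and be exited from the study". Sections 12.6.7 and 12.6.8.2 repeat the rule. The 12-month visit, with its angiogram, is scheduled only for subjects who were implanted.
- **Endpoint (8.1.1).** The count of "VRD treated aneurysms achieving Raymond Grade I (100% occlusion) at 12 months", with no retreatment, no parent artery stenosis above 50% and no target aneurysm rupture. Implant success is a separate secondary endpoint (8.1.2), recorded yes/no at the procedure (12.6.2).
- **Missing data (6.10, 6.2, 12.6.8.3).** Under 6.10, "the binary outcome for subjects who withdraw prior to the scheduled assessment will be derived using the Markov Chain Monte Carlo (MCMC) algorithm", assuming missing at random. Section 6.2 says that the study counts patients lost to follow-up as failures. Section 12.6.8.3 defines loss to follow-up as failure to reach the subject after three attempts for the 1-year visit.
- **Sample size (6, 6.3).** 119 treated subjects give "107 evaluable assuming a 10% loss to follow-up rate". No separate allowance is made for failed implants.

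**The concern.** A failed implant is known on Day 0 and is an outcome of the device. The protocol admits the subject to the primary set and then, by its own exit rule, ensures that the 12-month grade is never scheduled. An observed-data analysis so arranged estimates success among implanted subjects while carrying the label of all attempted subjects.

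The study has one arm and one formal efficacy test, so no control group offsets the effect. If subjects without an implant would not have been successes, dropping them always favours the device, and more so the harder it is to implant.

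**Working it through.** **Inputs from the protocol.** The test: "This hypothesis will be tested using an exact one sample binomial test at" one-sided 0.025 (6.2). The goal: "Therefore the historical success rate of 28% was selected as the historical control value" (6.3; 8.1.1 still prints 23%, and 28% is used here). The design target is "to have an 80% power with a significance level of 2.5"% at an expected rate of 41%, with 119 treated and 10% dropout.

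**Assumptions, not in the protocol.** The number of failed implants k among 119 is varied. Each implanted subject has a 10% chance of other loss. No non-implanted subject would be a success, and none is recorded as a failure by day 30.

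**Step 1: the plan's own figure.** Let c(n) be the smallest x with P(X ≥ x | n, 0.28) ≤ 0.025. For n = 107, c = 40, the attained level is 0.0221 and power at 41% is 0.804. This is the first n to reach 80%, and 107/0.9 = 118.9, rounded up to 119. The stated figures reproduce.

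**Step 2: an illustration.** With 10 of 119 not implanted, 109 × 0.9 ≈ 98 are observed.
- Dropped: 37/98 = 37.8%, exact lower limit 28.2%. This passes.
- Counted as failures: 37/108 = 34.3%, lower limit 25.4%. This misses; 41 successes would be needed.

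The example sits on the critical count, so it shows that a reversal is possible, not that it is likely.

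**Step 3: chance of passing when true success per attempt is 28%.** Success per implant is q = 0.28 × 119/(119 − k). The number observed, N, is Bin(119 − k, 0.9).
- Dropped: Σ P(N = n) · P(X ≥ c(n) | n, q)
- Counted as failures: Σ P(N = n) · P(X ≥ c(n + k) | n, q)

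| k | Expected observed | q | Pass, dropped | Pass, counted |
|---|---|---|---|---|
| 0 | 107.1 | 28.0% | 1.90% | 1.90% |
| 2 | 105.3 | 28.5% | 2.49% | 1.81% |
| 3 | 104.4 | 28.7% | 2.85% | 1.76% |
| 4 | 103.5 | 29.0% | 3.25% | 1.71% |
| 6 | 101.7 | 29.5% | 4.20% | 1.62% |
| 10 | 98.1 | 30.6% | 6.81% | 1.45% |
| 12 | 96.3 | 31.1% | 8.55% | 1.36% |

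The nominal 2.5% is exceeded from about 3 failed implants. With no other loss the pattern is the same: 4.8% and 10.0% for 6 and 12 failures when dropped, against 2.0% and 1.8% when counted.

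**Step 4: power.** The same sums with q = 0.41 give power if 41% is the rate per implant. With q = 0.41 × 119/(119 − k), 41% is the rate per attempt.

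| k | Dropped, 41% per implant | Counted, 41% per implant | Counted, 41% per attempt |
|---|---|---|---|
| 0 | 78.6% | 78.6% | 78.6% |
| 4 | 77.3% | 68.5% | 78.1% |
| 6 | 76.6% | 62.7% | 77.9% |
| 10 | 75.3% | 50.1% | 77.4% |

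The step from 80.4% to 78.6% at k = 0 comes from averaging over random dropout and has nothing to do with failed implants.

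**Step 5: could imputation correct it?** Apart from any early failures, every recorded 12-month outcome comes from an implanted subject. A missing-at-random model can draw only on those. Adding implant status as a covariate does not help, because no non-implanted subject has a 12-month grade from which to estimate its effect.

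**The case against.** Several objections have force.

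- **Section 6.2 counts losses as failures.** This is current text, so the protocol is inconsistent about missing outcomes and does not uniformly drop them. But the statement contradicts 6.5, and under 12.6.8.3 it does not reach subjects exited by rule.
- **Not every failed implant need be dropped.** The endpoint requires no retreatment or rupture, and the day-30 visit records further procedures and adverse events. A subject retreated or ruptured by then could be read as an observed failure. The protocol does not say so, and it would catch only some. A reader might infer that all non-implanted subjects are necessarily excluded; the text does not go that far.
- **Imputation.** A reader might infer that 6.10 gives these subjects the success rate of implanted ones. Section 6.10 speaks of subjects who withdraw and leaves the model variables to the SAP. Whether subjects exited by rule are imputed is unstated, and imputation assesses impact only.
- **The inflation is conditional.** It needs about 3 or more failures and a per-attempt target, whereas 8.1.1 speaks of treated aneurysms. Exclusion 3 and the expert angiogram review in 9.3 should limit failures. These points bear on size. They do not explain why 6.5 defines its set by attempted delivery.
- **Failures would not be hidden.** The implant-success percentage is reported. That helps a reader, but it does not enter the pass/fail test.

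**Conclusion.** The point holds as a gap in scoring. Sections 6.5, 12.6.5, 12.6.7 and 12.6.8.2 together place failed implants in the primary set and withhold the outcome needed to analyse them, and no current section counts them as efficacy failures. Under the stated assumptions the false-positive risk is about 3.3% to 8.6% for 4 to 12 failed implants among 119, against 1.9% with none and below 2% if they are counted.

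The size rests on an implant-failure rate that the protocol does not give; with 2 or fewer failures the nominal level is kept. The documents do not support saying that the error rate is certainly inflated. Nor do they support treating the smaller evaluable number as the main harm: under the observed-data analysis, power falls only from 78.6% to about 75% at 10 failures. The issue is which subjects the efficacy rate describes.

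**What to change.** - **6.5 and 8.1.1:** state that an ITT subject who leaves the index procedure without an implanted Barrel VRD is a primary efficacy failure, stays in the denominator, and is neither missing nor imputed. The observed-data rule then applies to implanted subjects only. Apply the same scoring to the Grade I or II secondary endpoint.
- **6.10:** exclude these subjects from imputation.
- **6.2:** reconcile the statement that losses are failures with the observed-data rule in 6.5.
- **6.3:** state whether 41% is per attempt or per implant, and restate power to match.

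No new data are needed, because implant success is already recorded on Day 0. The follow-up and exit schedule need not change.

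The cost is real. The reported success rate will be lower whenever implants fail. If 41% is per implant, power is about 69%, 63% and 50% with 4, 6 and 10 failed implants; if it is per attempt, power stays near 77% to 78%. A shortfall should be disclosed rather than met by enrolling more subjects.

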### **12.6.7 Study Exit**

Upon completion of the specified study follow-up at 12 months the subject will be exempt from further data collection. The subject will be seen by the treating physician according to standard care following intracranial aneurysm treatment. If the subject underwent attempted delivery with the Barrel VRD but did not receive a Barrel VRD implant, the subject will be exited from the study following the 30 day visit.

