### **12.6.8.2 Subject discontinuation by investigator**

An Investigator may discontinue a subject from the study, with or without the subject's consent, for any reason that may, in the Investigator's opinion, negatively affect the well-being of the subject. If a subject is withdrawn from the study, the Investigator will promptly inform the subject and Sponsor. If a subject is enrolled and undergoes attempted delivery with the Barrel VRD without successful implant of the investigational device, the subject will be exited from the study following the 30 day visit.

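### Subjects with a failed implant attempt are in the ITT set but exit after the 30-day visit, so the observed-data efficacy test leaves them out and becomes a test of implanted subjects

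*Protocol*

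**What the plan says.** - **Analysis set.** Protocol section 6.5 defines ITT as "all subjects who meet the study entry criteria, sign the written informed consent (enrolled), and undergo attempted delivery with the Barrel VRD". A failed attempt is therefore inside the primary set.
- **Exit rule.** Section 12.6.5 says that attempted subjects "but were not implanted should complete the 30-day visit and be exited from the study". Section 12.6.7 repeats that "the subject will be exited from the study following the 30 day visit". Section 12.6.8.2 applies the same exit to a subject who "undergoes attempted delivery with the Barrel VRD without successful implant of the investigational device".
- **Data used.** Section 6.5: "The primary analyses for both the safety and effectiveness endpoints will be based on the observed data".
- **Missing data.** Section 6.10 uses multiple imputation under missing at random to assess the impact of missing data: "an imputed dataset where the binary outcome for subjects who withdraw prior to the scheduled assessment will be derived".
- **Endpoint.** Section 6.2 defines success by Raymond grade at 12 months ± 8 weeks, without retreatment, parent artery stenosis above 50% or target rupture.
- **Conflicting text.** Section 6.2 also says that the study's ITT method counts patients lost to follow-up as treatment failures.
- **Known status.** Section 12.6.2 records implant success as yes or no for every procedure.

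**The concern.** The ITT definition brings failed attempts into the primary set. The exit rule then ensures that no 12-month grade is scheduled for them, and the observed-data rule removes subjects without one. A set named ITT becomes, in the efficacy test, implanted subjects with a 12-month outcome. A device that could not be placed in some patients would be judged only on those in whom it was placed.

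The goal of 28% was not built that way. It comes from a historical rate of 37/87 in Table 6-1, which divides by the whole cohort although only 63 of the 87 had angiographic follow-up. Section 6.2 also cites counting losses as failures as a reason why the literature rates are not directly comparable. Dropping subjects on the Barrel side runs against both. At stake is the pass/fail conclusion on the primary efficacy endpoint.

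**Working it through.** **Inputs from the protocol.** Exact one-sample binomial test, one-sided alpha 0.025 (6.2). Goal 28%, power 80%, expected success 41%, 107 evaluable, 10% dropout, 119 treated (6, 6.3, Table 6-2).

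**Assumed input.** Implant-failure fraction f. The protocol gives none, so 5%, 10% and 15% are shown.

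**Step 1: reproduce the design.** With n = 107, the smallest x with P(X ≥ x | 0.28) ≤ 0.025 is 40. The actual level is 0.0221 and power at 0.41 is 0.804. 107/0.90 = 118.9, so 119. The stated figures reproduce.

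**Step 2: error when failed implants are dropped.** Let the true success rate over all attempts be 28%, with a failed implant counted as a non-success. The rate among implanted subjects is then 0.28/(1−f). Of the 107 who would otherwise be evaluable, n = round(107(1−f)) remain. The test uses the critical value c for that n.

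| f | n | c | Level at 28% among implanted | Rate among implanted | Error, P(X ≥ c) |
|---|---|---|---|---|---|
| 5% | 102 | 39 | 1.6% | 29.5% | 3.6% |
| 10% | 96 | 37 | 1.6% | 31.1% | 7.4% |
| 15% | 91 | 35 | 2.0% | 32.9% | 15.6% |

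The fourth column is the matched actual level of the same test, so the inflation is from 1.6–2.0% to 3.6–15.6%. At f = 2% (n = 105, c = 40) the error is 2.2%, so on this base a very low failure rate does not take the error above nominal. With 119 attempts and no other loss, 6, 12 or 18 failed implants give 4.8%, 10.0% or 18.8%.

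**Step 3: a single borderline result.** The smallest pass is 40/107 = 37.4%, with exact lower limit 28.2%. Counting one failed implant gives 40/108 = 37.0%, lower limit 27.9%, which no longer exceeds 28%.

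**Step 4: power.** If 41% holds among implanted subjects only, the rate over all attempts is 0.41(1−f). Counting failures keeps n = 107 and c = 40.

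| f | Rate over all attempts | Power, failures counted | Power, failures dropped |
|---|---|---|---|
| 0 | 41.0% | 80.4% | 80.4% |
| 5% | 39.0% | 66.5% | 74.7% |
| 10% | 36.9% | 49.5% | 72.2% |
| 15% | 34.9% | 32.4% | 72.4% |

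**Step 5: imputation.** If a day-30 exit is handled as an early withdrawal, a missing-at-random model can only borrow from implanted subjects, because no 12-month outcome is scheduled for anyone else. Adding implant status as a covariate does not supply one. At 10% of 119 (12 subjects) and a 41% draw rate, 12 × 0.41 = 4.9 complete occlusions would on average be credited to subjects without the device.

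**The case against.** - **The target may be treated aneurysms.** Section 8.1.1 words the endpoint over Barrel-treated aneurysms, and no section calls a failed implant an efficacy failure by definition. For that target, the test among implanted subjects keeps its level (1.6–2.0% above). This stands as a reading of 8.1.1, but section 6.5 names the all-attempts ITT set as primary. The protocol has not chosen between them.
- **Section 6.2 may already count them as failures.** It contradicts the observed-data rule, so it settles nothing. Section 12.6.8.3 defines lost to follow-up as unreachable for the 1-year visit, which does not describe a mandated exit at day 30.
- **Imputation is supportive.** Correct: observed data are primary, so a reader should not infer that imputed successes enter the primary test. Section 6.10 speaks of subjects who withdraw, and the SAP could still exclude mandated exits.
- **Other known failures.** A reader might infer that retreatment or rupture without a 12-month image is dropped in the same way. The text does not support that: absence of both is part of the endpoint, and subsequent procedures and adverse events are collected at every visit. Only neurological death before imaging is left unclear.
- **Safety.** A reader might infer that the day-30 exit lowers the safety rate. It would if these subjects stay in the denominator as event-free. If event-free ones are dropped and early events kept, the rate rises. The protocol does not say which applies.
- **Size.** No implant-failure rate is given, so the figures are conditional.

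**Conclusion.** The point holds for primary efficacy. Read together, sections 6.5, 12.6.5, 12.6.7 and 12.6.8.2 remove failed implants from the test that section 6.5 calls ITT, and section 6.2 says something different about losses. If success over all attempts is the target and 5%, 10% or 15% of attempts fail, the one-sided error at a true rate of 28% is 3.6%, 7.4% or 15.6%. These figures assume that other dropout is unrelated to implant success. The bias is zero with no implant failures and small at about 2%. A borderline pass can be reversed by one failed implant. For safety, the finding is only that the 12-month endpoint in section 6.6 and the day-30 exit do not match.

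**What to change.** 1. In sections 6.5 and 6.10, state that an ITT subject with attempted delivery and no Barrel implant is an observed non-success in the primary efficacy analysis and is not imputed.
2. In the same place, confirm that failures known before the 12-month image (retreatment, target rupture, neurological death) are scored as failures and not imputed.
3. Reconcile section 6.2 (losses are failures) with section 6.5 (observed data), and align the endpoint wording in section 8.1.1 with the ITT set.
4. In section 6.3, state that the 41% applies to all attempts, or restate power with an explicit implant-failure rate.
5. Reconcile section 6.6 with the day-30 exit, and have the report state how subjects with truncated follow-up enter the safety denominator. Any added follow-up has to allow for the stroke component, which rests on an NIHSS change; the 30-day evaluation that may be done by telephone includes only the modified Rankin score.

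**Cost.** Items 1 to 3 are wording. Item 4 may cost real power: if 41% describes implanted subjects only, 107 evaluable subjects give about 66%, 50% or 32% at 5%, 10% or 15% implant failure, and the sample size or the assumption would have to be revisited. Item 5 is wording if only the denominator rule is stated, and more if follow-up is changed.
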